### **Possibility of discovering a subject's previously unknown condition**

We will use a set of safety procedures to ensure safe participation during the research trial. The research team has medical personnel on staff nearby (i.e. Duke University Medical Center) that are available to deal with any unforeseen medical complications that may arise.

The research team will assess medical and psychiatric safety, treatment compliance, and data completion for each subject. We will deal with psychological problems or distress should it arise. If necessary, we will contact patients' providers using a ROI to connect them with the patient in distress.

Consistent monitoring of participant progress provides one level of safety procedures. Another level of safety procedures involves evaluation of data collected (especially items related to aggression/suicidality in the BSI) and of verbal reports of suicidal and/or homicidal intent to staff members. All reports of suicidal or homicidal ideation will be immediately reported to the PI as well as to the patient's treating clinician. All research staff will receive training in identifying suicide/homicide risks and/or signs of dangerous intoxication and in following the steps needed to appropriately respond to these signs.

Participants judged by study investigators at any point to be a danger to self or others or who are judged to be in grave danger due to continued drug use and/or to medical/psychiatric problems will be discontinued from the study but actively connected with their treating clinician.

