#### Secondary Outcomes:

- (1) Cigarettes per day (CPD) will be measured daily with the tracking feature embedded within each app. LTQ contains a feature that allows users to enter how many cigarettes they smoked at the end of the day
- (2) Quit attempts defined as self-reported no smoking at all for 24 hours, and time to 7-day relapse will be assessed via a Timeline Follow Back interview at Weeks 4, 8 and 12
- (3) 7-day point prevalence abstinence will be determined by responses to a standard self-report item (i.e., not smoking even a puff of a cigarette within the last 7 days) and breath CO<5 ppm at Week 12
- (4) Adherence to NRT will be measured daily with the app tracking feature, as well as brief interviewer-administered questionnaires at Weeks 4, 8, and 12
- (5) Participant Safety will be assessed by monitoring all adverse events during the 12-week period and in close collaboration with their medical providers

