## 4.0. Study Overview

- 1. Eligibility and Consent:** PLWH who provisionally qualify based on a phone screen will be invited to attend a remote Zoom screening visit. Informed consent will be obtained, and participants' interest in quitting, HIV and smoking statuses will be evaluated. Individuals will be screened to ensure that they own an Apple or Android smartphone, are not pregnant (if female), and are medically eligible to use NRT. Our study physician will evaluate their medical eligibility. In addition, we will obtain a signed Release of Information from potential participants to closely work with their own medical providers to monitor adverse events, dispensing of NRT, and overall participant safety.
- 2. Randomization:** Participants will be allocated to conditions using 1:1 randomization.
- 3. Interventions:** Participants will be assigned to LTQ-H or NCI QuitGuide. All participants will receive a standard 8-week course of NRT (transdermal nicotine patches starting at 21mg/24h) following recommendations contained in the U.S. Clinical Practice Guidelines.
- 4. Background Analytics:** Research staff will instruct participants on how to install the study app onto their personal smartphones and will tell them how to add a study ID in the app that will be used to retrieve background analytics information (Google Analytics) from both the LTQ-H and NCI QuitGuide apps.
- 5. Follow-Up Visits:** Visits will occur at 4, 8 and 12 weeks post-randomization. During these visits we will assess smoking and smoking abstinence, new or changes in existing adverse events and user experience with the assigned app. We will biochemically verify self-reported smoking abstinence at week 12.

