### 6.3. Baseline Visit

Participants will attend a Zoom baseline session following their eligibility determination to be randomized to the intervention. A few measures will be completed prior to randomizing the participant:

- (1) Health Changes questionnaire (adverse event and con med forms filled out if applicable)
- (2) COVID-19 & Quitting smoking Questionnaire (Adapted)
- (3) Assessing psychiatric functioning
  - a. Depression Anxiety Stress Scale-21 (DASS-21)
  - b. C-SSRS
  - c. Brief Symptom Inventory (BSI)
- (4) Fagerström Test for Nicotine Dependence (FTND)
- (5) Timeline Follow-Back (TLFB) Questionnaire
- (6) Drug Use Questionnaire (1 Month)
- (7) Internet/Smartphone Access and Use survey

After completing these measures, the participant will be randomized. They will receive either the LTQ-H app, or a standard-of-care app called QuitGuide developed by the National Cancer Institute (NCI). The RA will instruct

the participant on how to download their assigned app from the App Store/Google Play Store. The RA will give a brief overview of the assigned app to discuss the main functions and troubleshoot any major issues that may arise. They will also instruct the participant to enter their unique tracking code (similar to their subject ID) to allow us to track their background analytics data.

Following the baseline visit, we will mail 8 weeks of NRT patches to participants. We will tell participants to call/email the study team to confirm that they received their NRT. We will then instruct participants to start using the patches on the day of their quit date, which will be within 4 weeks of the baseline visit. Participants will be oriented on the best practices of using NRT based on the package instructions. There will be a brief compliance review session following the instructions in order to ensure that patients understand how to use the medication.

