#### 6.4. Follow-Up Visits

Participants will complete monthly follow-up (FU) visits at Weeks 4, 8, and 12 weeks post-randomization. All visits will be conducted via zoom video calling.

At each visit, participants will complete surveys to assess their smoking behavior, changes in physical or mental health (which will prompt staff to assess for adverse events), and user experience with their assigned study app. See table below for a list of all the measures.

At each visit, research staff will conduct an interview with the participant to ask about their experience using their assigned app. This interview will be audio recorded for later review. Each FU visit is expected to last between 45-60 minutes, depending on the assessment burden.

Measure	Week 4	Week 8	Week 12
Biochemical Verification (CO)			x
Health Changes Questionnaire	x	x	x
Adverse Events and Con Meds (if applicable)	x	x	x
COVID-19 & Quitting Smoking Questionnaire (Follow-up)	x	x	x
Drug Use Questionnaire (1 Month)	x	x	x
Timeline Follow-Back	x	x	x
DASS-21	x	x	x
BSI	x	x	x
Systems Usability Scale (SUS)	x		x
Qualitative user experience interview	x		x
Research Participant Perception Survey (RPPS)			x

Participants who self-report smoking abstinence by the final follow-up visit (FU3) will be mailed an iCO smokerlyzer device to do a breath test in order to biochemically verify abstinence. We will mail these to participants following their FU3 session. Once they receive the device, we will set up a short Zoom call to walk them through the CO breath test process. Staff will be on the call in order to ensure that it is the participant

who is doing the test, and that they are doing the test properly. Once the participant completes the test, we will ask them to email the result of their test to our lab email. Participants will keep these devices once they are completed in the study. The stop date for these participants will be the date of this breath test instead of the date of the FU3 visit.

Background analytics will be collected throughout the 4 months of participation, and will be measuring some things such as CPD, mood ratings, NRT use, duration of app use, and number of interactions within the app.

At the final visit (Week 12), participants will be given quitting resources if they have not quit. They will also be referred to other research studies, if eligible and willing.

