## 6.5. Compensation

Participants will be compensated for their participation in the trial. Participants can earn up to \$130 for completing all study activities. Compensation amounts are determined based on the burden of the research activities at the time point, as well as the length of the visit. Compensation will be provided on a Duke ClinCard that will be given out at the screening visit. Any withdrawn participants will be compensated for any research activities that were completed. In addition to monetary compensation, participants will be given an 8-week supply of NRT patches free of charge.

Assessment Time Point	Compensation Amount
Screening	\$15
Baseline	\$15
Week 4	\$20
Week 8 (Via telephone)	\$30
Week 12	\$50
Total	\$130

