#### Minimizing risk of harm and protecting participants' rights and welfare

To address the possible side effects from Nicotine Replacement Therapy (NRT) patches, we will have our study doctor, [name], available to monitor and evaluate participants' use of NRT in addition to consulting with the research team. We will also emphasize the package instructions' directions of placing the NRT patch in varying locations, and replacing the patch every morning to reduce possible skin irritation. The

research team will monitor use of the NRT as well as review any reported changes in medications by the subject throughout the course of their participation.

Potential participants will be screened to eliminate candidates with disorders or conditions that are contraindicated with the intervention (see section 2.1), or those who are not able to provide informed consent. We will work to coordinate the subject's participation in the study with the medical/mental health care that they are already receiving by obtaining a written Release of Information (ROI) that will allow research staff to communicate with their providers throughout the study.

The research team will be sensitive to issues surrounding confidentiality and other forms of participant risk by taking steps to maintain confidentiality and reduce the risk of unauthorized disclosure of subject data. For instance, we will use a research subject identification number (subject ID) as the identifier for research data rather than using personally identifiable information (PII), and any forms/data containing PII will be stored separate from research data. We will emphasize the confidential nature of the data collected in this trial, explaining our safeguarding procedures to potential and enrolled research subjects. We will note which de-identified data will be shared, and how we work to ensure its security.

If at any time a participant expresses discomfort over any aspect of the study procedures, the research team member may discontinue the distressing activity.

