### Collecting and recording AEs

We will be tracking all AEs and serious adverse events (SAEs) that a participant may experience once starting the study intervention (from Baseline onward). We will be doing this throughout the study, regardless of whether or not we think they are related to the study intervention. AEs will be documented by research personnel during research assessments, or at any other time during the clinical trial that they have contact with or about the subject. The PIs and study doctor are responsible for oversight on AEs.

We will document each AE with details such as:

- Description of event;
- Start and stop dates (if applicable);
- Whether or not they are getting treated (e.g. medications or therapies);
- Whether or not it is considered an SAE;
- Any other pertinent details.

Collected AEs will be documented and recorded with the information above on AE forms and entered into an electronic database (i.e., REDCap). On a weekly basis, the PI will review each AE to determine the following:

- Relationship to the study intervention;
- Severity of the event;
- Outcome;
- Status: ongoing, closed, lost to follow-up;
- Deciding what course of action should be taken to address the AE.

The PI may consult with the study physician if needed.

If the participant reports a SAE, the same collection and recording procedures will take place as with AEs. However, research staff will alert the PI to the SAE as soon as possible (within 24 hours of a reported SAE). The PI will review the reported SAE within 24 hours of becoming aware of it. SAEs will have a separate form completed for each one that's reported.

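### Participants judged to be in danger are removed from the study, and nothing separates stopping treatment from ending safety and outcome follow-up

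*Combined protocol and SAP*

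**What the plan says.** The rule is in section 7.1, under the heading on discovering a previously unknown condition. If the investigators judge, at any point, that a participant is a danger to self or others, or is in grave danger from continued drug use or medical or psychiatric problems, the participant "will be discontinued from the study but actively connected with their treating clinician". The wording is mandatory and refers to the study as a whole.

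Other text that bears on it:

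- Section 2.2, secondary outcomes: "Participant Safety will be assessed by monitoring all adverse events during the 12-week period and in close collaboration with their medical providers".
- Section 6.4: each follow-up visit includes surveys on "changes in physical or mental health (which will prompt staff to assess for adverse events". Visits are at Weeks 4, 8 and 12.
- Section 7.1, on minimizing risk: if a participant is uncomfortable, "the research team member may discontinue the distressing activity". This is a narrower step than leaving the study.
- Section 6.5, the only text on withdrawn participants: "Any withdrawn participants will be compensated for any research activities that were completed".
- Section 4.0: a Release of Information lets staff "closely work with their own medical providers to monitor adverse events, dispensing of NRT, and overall participant safety".
- Section 7.2: AEs are recorded at assessments or at any other contact with, or concerning, the participant during the trial. The principal investigator's weekly review includes "Deciding what course of action should be taken to address the AE".
- Section 6.3: "Following the baseline visit, we will mail 8 weeks of NRT patches to participants".

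**The concern.** Stopping a treatment and stopping observation are different decisions, and the protocol has one instruction for both. Staff who follow section 7.1 as written would reasonably cancel the remaining visits. Those visits are where AEs are actively asked about. After removal, a new event (as opposed to the one that triggered removal) reaches the study only if a provider or the participant raises it, or if staff choose to ask.

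Three things are at stake. First, scheduled safety data would stop for the participants whom the investigators regard as most at risk, despite the 12-week commitment in section 2.2. Second, the AE total that section 8.2 compares between arms would cover a shorter period for these participants. Third, their Week 12 data would be missing: the usability score and end-of-treatment interview, which belong to the primary acceptability outcomes, and verified abstinence, which is secondary.

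**Working it through.** The plan gives no figure on this point, so there is none to reproduce. The check is a comparison of texts, with simple counts per removal.

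**1. Does any text keep a removed participant in follow-up?** Section 7.1 removes the person from the study and hands over to the treating clinician. Section 6.4 sets out visits without mentioning discontinued participants. Section 6.5 covers payment for completed activities only. Section 7.2 allows AEs to be recorded from any contact but does not require contact after removal. No section provides for visits or active AE follow-up after removal.

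**2. Scheduled AE assessments lost.** The section 6.4 table puts the Health Changes Questionnaire at Weeks 4, 8 and 12. Section 5.2 says that this questionnaire asks about AEs, so there are 3 scheduled assessments. Weeks 4 and 8 are used as examples because section 7.1 names items of the Brief Symptom Inventory as a safety signal and that inventory is given at those visits.

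- Removal at the Week 4 visit: 3 − 1 = 2 of 3 assessments lost; 12 − 4 = 8 of 12 weeks unobserved by schedule.
- Removal at the Week 8 visit: 3 − 2 = 1 of 3 lost; 12 − 8 = 4 of 12 weeks.

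**3. Week 12 outcomes lost.** Removal at either visit loses the Week 12 usability score, interview and abstinence assessment. I give no count of all skipped measures, because the schedules conflict. Section 5.2 puts the usability scale at each follow-up, and the prose of 6.4 puts an interview at each visit, but the 6.4 table marks both at Weeks 4 and 12 only. Section 5.2 also places the nicotine dependence test at monthly follow-ups, and the table omits it.

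**4. Share of the data.** One removal is 1/30 = 3.3% of an arm, or 1/60 = 1.7% of the trial.

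**5. Patches still held.** Assume daily use from a quit date 0 to 4 weeks after baseline (section 6.3). Weeks of supply left = 8 − (removal week − quit week).

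- Week 4: 8 − (4 − 0) = 4, up to 8 − (4 − 4) = 8.
- Week 8: 8 − (8 − 0) = 0, up to 8 − (8 − 4) = 4.

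**6. Payments remaining (section 6.5).** $30 + $50 = $80 after Week 4; $50 after Week 8.

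**The case against.** The strongest reply is that the loss of follow-up is inferred. The protocol never says that safety monitoring stops. Section 2.2 makes no exception for removed participants and names the medical providers as partners. The Release of Information has no stated end at removal. Section 7.2 accepts reports from any contact and requires each recorded AE to be given an outcome and a status. Ending research demands on someone in crisis, with an active clinical handover, also puts welfare first.

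Much of this stands. A reader might infer that the protocol abandons safety monitoring of its highest-risk participants. The documents do not support that. The triggering event, once recorded, is reviewed and acted on, and provider-reported events remain possible. What is missing is any requirement to look for later events, and any provision for the remaining scheduled assessments.

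A reader might also infer that patches left in the participant's hands are an unmanaged hazard. That too goes beyond the text: a study doctor is available to evaluate patch use, the principal investigator decides the action for each AE, and the clinician is brought in. An explicit instruction would be tidy, but its absence is not a defect on its own.

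The effect on the analysis is slight. Primary outcomes are descriptive or thematic. For the yes/no AE outcome, a participant whose trigger was recorded as an AE already counts as yes; only the AE total can fall short.

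**Conclusion.** The point holds as a minor one. As written, the rule ends visit-based AE assessment (2 of 3 or 1 of 3 assessments in the two examples) and Week 12 outcomes for each person removed. This sits poorly with the commitment to monitor all AEs for 12 weeks. AE capture through providers remains open but is not required.

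This rests on the plain meaning of discontinuation from the study, and on the body of the protocol alone; the consent and Release forms are not in the file and may say more. The expected number of removals is not given. It is probably small in a 60-person trial that screens for unstable substance use, suicidality and medical eligibility. A reader might infer bias between the arms, but nothing in the documents suggests that removals would differ by arm.

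**What to change.** In section 7.1, replace removal from the study with discontinuation of the app, the patch or both, as the clinical team decides, and keep the handover to the treating clinician. Add that, with the participant's agreement and where clinically appropriate, AE and serious AE follow-up continues to Week 12 by brief contact or provider report. Week 12 outcome assessments are offered but not required.

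The cost is a small amendment with ethics review, a check that the consent and Release wording covers the continued contact, and a few extra contacts, which the participant can decline or the clinical team can waive. The visits and payments are already in the plan: at most $80 per person after a Week 4 removal and $50 after a Week 8 removal. Who comes off treatment does not change.

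Two clarifications are optional: a line telling removed participants whether to stop or continue patches they hold, and separate reporting of investigator-initiated discontinuations in the descriptive retention results, which needs a reason field in the database.

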### **Anticipated benefits of research on individual subjects**

Participants might benefit from the study by quitting smoking. We will provide free nicotine replacement therapy patches to participants, and the monitored use of the smoking cessation apps may contribute to cessation.

### **Anticipated benefits of research on society, benefits outweighing risks**

Smoking directly causes 480,000 deaths a year in the United States. The prevalence of smoking among PLWH is disproportionately high (42-43%) as compared to the U.S. general population (15%). Increased longevity among PLWH—due to the development of highly effective treatments for HIV infection—has resulted in PLWH losing more years to smoking than to HIV infection itself.

Information derived from the study could help improve the effectiveness and reach of smoking cessation treatments for PLWH. This may benefit society and other clients of treatment programs. Participants in the study may see improvement in the physical, psychological, occupational, familial, and economic problems associated with their tobacco cessation.

The interviews proposed in this research may guide the development of tools to treat tobacco addiction in this population. Given that levels of access to mental health providers depends on geographical location, this study may help develop low-cost and high-reach smoking cessation tools for PLWH in areas where there may be few or lacking smoking cessation services (e.g., rural areas). Therefore, the minimal risks to participants are reasonable in relation to the anticipated benefits.

## 7.2. Adverse Event Collection & Reporting

### Anticipated events

Given that many people who are HIV+ and smokers have more medical needs than the general population, we do anticipate subjects will report a higher rate of Adverse Events (AEs) as an inherent characteristic of this population. These include such events as COPD, lung cancer, pneumonia, psychiatric symptoms, and Antiretroviral Therapy medication side effects.

Some anticipated AEs resulting from the study interventions include study drug side effects. The study drug (i.e. NRT) has some common side effects that we expect subjects to occasionally report, including: dizziness, headaches, rapid heart rate, increased blood pressure, nausea and diarrhea. For the nicotine patch in particular, common side effects include skin irritation and/or itching where the patch is placed, insomnia, and vivid dreaming.

In addition, quitting smoking can result in withdrawal symptoms that may be uncomfortable to the participant. Common withdrawal symptoms include: cravings for cigarettes; depressed or sad mood; insomnia or trouble sleeping; feeling irritable, on edge, or grouchy; trouble concentrating; restlessness; decreased heart rate; and increased appetite/weight gain.

There may be some risks associated with smartphone and app usage. Events that we anticipate subjects may report to us around using the study smartphone include sleep disturbances (from high frequency use), eye strain (from viewing the screen), and data breaches (if subjects enter their personal information in the phone).

